### ***Study Outcomes***

#### **Primary Feasibility Outcome**

The primary feasibility outcome is patient recruitment rate over the one-year study period. We will also measure adherence to the protocol for this pilot study. This pilot is not powered to determine differences in treatment groups; however, a priori outcome definition and accurate outcome assessment is needed to inform the future study.

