#### **Efficacy Outcomes**

We also have efficacy outcomes consistent with those used by the previous study by Self et al.:

**Primary outcome:** time to DKA resolution (hours), defined as the time elapsed between ED presentation and ketoacidosis resolution, following criteria from the American Diabetes Association Consensus Statement on Hyperglycemic Crises (plasma glucose <11.1 mmol/L and two of: plasma bicarbonate ≥15mmol/L, venous pH >7.3 or anion gap ≤12mmol/L).

\*Of note, Diabetes Canada's guidelines lack definitive criteria for DKA resolution, only stating that insulin infusion should continue until ketosis resolves (measured by "normalization of plasma anion gap"). Following Self et al., patients discharged prior to evidence of laboratory criteria for DKA resolution will be classified as having DKA resolution at time of discharge.

**Secondary outcomes:** time to insulin infusion discontinuation (hours), intensive care unit admission, in-hospital death, hospital length of stay (days), hyper- or hypokalemia (>6.0 or <3.0 mmol/L) post-ED, in-hospital acute kidney injury post-ED (Stage 2 or greater – defined as serum creatinine increase >200% from baseline or <0.5mL/kg/hr urine output for <12 hours) and major adverse kidney events within 30 days, defined as a composite of: i) death, ii) new renal replacement therapy, or iii) final serum creatinine ≥200% baseline at the earliest of hospital discharge or 30 days after ED presentation).

Our hospital's DKA protocol involves hourly point-of-care glucose checks and bloodwork (electrolytes, including anion gap, and venous blood gas) every two hours while receiving insulin infusions. Patient characteristics and clinical/laboratory data will be collected via our electronic medical record. All outcomes listed above can be ascertained via health records review, which will occur at 1,3,7, and 30 days post-enrolment.

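### The secondary acute kidney injury outcome caps the duration of low urine output and sets no minimum, which does not fit its Stage 2 or greater label; the creatinine limb should be clarified in the same edit

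*Combined protocol and SAP*

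**What the plan says.** In the combined protocol and SAP, the secondary outcomes under Efficacy Outcomes include "in-hospital acute kidney injury post-ED (Stage 2 or greater", followed at once by the defining rule: "serum creatinine increase >200% from baseline or <0.5mL/kg/hr urine output for <12 hours". The same sentence goes on to a 30-day kidney composite, whose creatinine component is "final serum creatinine ≥200% baseline at the earliest of hospital discharge or 30 days after ED presentation".

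The section describes the source of the outcome set this way: "We also have efficacy outcomes consistent with those used by the previous study". Outcomes are to be taken from health records review, "which will occur at 1,3,7, and 30 days post-enrolment".

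Under Primary Feasibility Outcome the protocol sets its own standard, that "a priori outcome definition and accurate outcome assessment is needed to inform the future study", and also limits what the comparison of arms can show: "This pilot is not powered to determine differences in treatment groups".

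No other section restates or corrects the AKI definition, and there is no staging table.

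**The concern.** A label of Stage 2 or above is a severity floor with no ceiling. One would expect the rule beneath it to set a minimum that an episode must reach. The urine limb, "<0.5mL/kg/hr urine output for <12 hours", does the opposite: it limits how long the low output may last and does not say how long it must last.

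An abstractor who follows the text would record a short dip as an event and might discard prolonged low output. The Data Analysis section plans no adjudication committee for the pilot, so no such body would settle the wording. Study Objective(s) hypothesizes faster resolution without more adverse outcomes, and AKI is one of the listed outcomes that bear on this. An uncorrected definition could also be carried into the planned 516-participant trial that the pilot is meant to inform.

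The creatinine limb raises a smaller question. A percentage increase from baseline and a percentage of baseline are different quantities, and the wording leaves room for a reader to take one for the other.

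**Working it through.** The plan states no figure that depends on this definition, so there is nothing to reproduce. The check is a reading of the rule plus percentage arithmetic. All inputs come from Efficacy Outcomes: the severity label, the urine rate (below 0.5 mL/kg/hr), the duration limit (under 12 hours), the AKI creatinine wording and the composite's creatinine wording.

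**Urine limb.** Let d be the length in hours of a spell below 0.5 mL/kg/hr.

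- Reading A, the limit is total episode length: the limb is met if 0 < d < 12 and is not met if d ≥ 12.
- Reading B, the limb is met once a spell is under way and has not yet reached 12 hours: every spell passes through that state, so it is met for all d > 0.

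For illustration only (these lengths are chosen here and are not in the documents):

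| Spell length | Reading A | Reading B |
|---|---|---|
| 1 h | counts | counts |
| 11 h | counts | counts |
| 12 h | does not count | counts |
| 24 h | does not count | counts |

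Under A, a 24-hour spell enters the outcome only if creatinine also qualifies, while a 1-hour spell enters without it. Shorter episodes are kept and longer ones dropped, the reverse of a floor with no ceiling. Under B nothing severe is lost, but the 12-hour figure does no work. Neither reading has a minimum duration.

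Reversing the sign under A (d ≥ 12, shown only to gauge how much hangs on it) moves every spell to the other side: those under 12 hours stop counting and those of 12 hours or more start to count.

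**Is the symbol an artefact of text extraction?** It is unlikely. The same section prints ≥ for bicarbonate and for the composite's creatinine, and ≤ for the anion gap. The printed page should still be checked.

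**Creatinine limb.** Let B0 be baseline creatinine.

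- An increase of more than 200% from baseline, taken literally: value > B0 + 2 × B0 = 3 × B0.
- Read as more than 200% of baseline: value > 2 × B0.
- Composite, at least 200% of baseline: value ≥ 2 × B0.

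| Multiple of baseline | AKI, literal (> 3) | AKI, alternative (> 2) | Composite (≥ 2) |
|---|---|---|---|
| 1.9 | no | no | no |
| 2.0 | no | no | yes |
| 2.5 | no | yes | yes |
| 3.0 | no | yes | yes |
| 3.1 | yes | yes | yes |

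The two AKI readings differ for values above 2.0 and up to 3.0 times baseline. With an assumed baseline of 80 µmol/L, the cut-off is 240 or 160 µmol/L.

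**The case against.** A reader might infer that the urine rule contradicts its label however it is read. The documents do not support that. They define the stage only through this clause. On reading B no long spell is lost, so the open upper end of the label is respected. To call a brief dip too mild for Stage 2 one needs a staging system that the protocol does not reproduce. On the text alone, only reading A contradicts the label; reading B leaves an idle clause. Nor is it certain that a short dip would be recorded: an assessor working from the label, and treating the sign as a slip, might never apply the literal rule.

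A reader might also infer that the AKI and composite creatinine criteria contradict each other. They are different outcomes, one an in-hospital increase and the other a final value at discharge or day 30, and their cut-offs may differ on purpose. What stands is an ambiguity in the AKI wording.

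A third inference would be that harm is done unless the text is corrected by the day-1 review. This is not shown. Outcomes come from electronic medical records, and if the underlying values are there, cases can be reclassified before analysis. The documents also do not show how often the urine limb would operate: the monitoring described covers glucose, electrolytes and venous gas, and urine output is not among the examples under Data Collection. That list is illustrative, so this does not show that urine output goes uncollected.

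These objections narrow the point. They do not remove it: the rule as printed has a maximum and no minimum, and nothing elsewhere corrects it. The reference to a previous study tells the sponsor where to look, but does not state the rule.

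**Conclusion.** The urine limb is wrong as written, and the point is minor. Read as total episode length, it counts brief dips and excludes low output of 12 hours or more unless creatinine qualifies, against its own label. Read as met early in any spell, its duration clause has no effect. Either way the protocol falls short of the advance definition it asks of itself. The creatinine limb is ambiguous between more than 2 and more than 3 times baseline, and no more than that.

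The effect on the AKI count cannot be computed, because the documents give neither an AKI rate nor urine data. The impact is confined to one secondary outcome in a 52-participant pilot that is not powered for treatment differences. Recruitment, time to DKA resolution and the sample size are unaffected. The conclusion assumes that the printed sign is as extracted; if the page shows otherwise, the urine point falls and the creatinine point remains.

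**What to change.** Before outcome data are analysed, and preferably before abstraction starts so that charts need not be revisited:

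1. Reconcile the urine limb with its label by restating it as a minimum duration. Twelve hours is the only figure the protocol gives, and it should be confirmed against the staging source the sponsor intended.
2. In the same edit, write the creatinine limb as an explicit multiple of baseline with its inequality sign, confirmed against that source.

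The cost is a one-line correction to one secondary outcome definition. Sample size, randomization and treatment do not change. If any charts have already been abstracted, AKI should be reclassified under the corrected rule.

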#### ***Sample Size***

The full-scale multi-centred will include 516 participants (258 per arm), assuming  $\alpha=0.05$ , power=80%, 1:1 allocation, a 40% (6.76 hours) minimal clinically important reduction in DKA resolution time, and 10% attrition rate. This trial will be conducted at 6 ED sites over 2 years. Based on this, the sample size for this local pilot RCT is 52 participants (26 per arm).

#### ***Sample size for Full-Scale Trial***

The sample size calculation for this trial was based on a study of Clinical Effects of Balanced Crystalloids vs Saline in Adults with Diabetic Ketoacidosis which compared the clinical effects of balanced crystalloids with the clinical effects of saline for the acute treatment in DKA in two clinical trials (Isotonic Solutions and Major Adverse Renal Events Trial [SMART] and the

Saline Against Lactated Ringer's or Plasma-Lyte in the Emergency Department [SALT-ED]10). The primary outcome for this comparison was the time between ED presentation and DKA resolution, measured in hours. Self et al. (2020) found an absolute reduction in time to DKA resolution of 3.9 hours. In the balanced crystalloids group (n=94), the median time to resolution of DKA was 13.0 hrs [IQR: 9.5-18.8], while in the saline group (n=78) the median time to resolution was 16.9 hrs [IQR: 11.9-34.5]. The IQR was used to calculate the standard deviation for each group based on the following assumption for normally distributed data:  $SD=IQR/1.35$ . The pooled standard deviation was then calculated based on the sample size and standard deviation of each group from the Self et al. (2020) study [ $\sqrt{((n1-1)*SD1^2 + (n2-1)*SD2^2)/(n1+n2-2)}$ ] and was determined to be 12.37. To establish superiority of balanced crystalloids versus saline in the time to resolution of DKA, a superiority margin for a clinically significant difference was chosen to be a 40% (=6.76 hours) reduction in time to resolution of DKA based on expert consensus and patient partner feedback. A conservative attrition rate of 10% was selected for the sample size calculation, as loss to follow-up rates should be low given the nature of the intervention (IV fluids) and follow-up period (<24 hours). The actual attrition rate determined by this pilot study will inform the sample size calculation for the full-scale multicentre study. Therefore, to achieve 80% power at the 5% level of significance with equal allocation, the sample size for the balanced crystalloids (Ringer's lactate) group and the saline group, while accounting for a 10% loss to follow up and a 25% reduction in time to DKA resolution, is 516 participants (258 per group). The sample size was calculated using Wang and Ji's (2020) method for common clinical study designs available at <http://riskcalc.org:3838/samplesize/>.

We plan to conduct the full-scale trial at 6 ED sites over 2 years, which would require an average minimum recruitment of 86 participants per site (43 per site per year). Our research group has established relationships with these other Canadian EDs where we have previously conducted successful studies. If further sites are needed for recruitment, we will leverage the Network of Canadian Emergency Researchers (NCER).

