### **Randomization, Blinding, Allocation Concealment**

Enrolled patients will be block randomized to treatment or comparator in a 1:1 allocation ratio. The block size will be unknown to investigators and those involved in patient care and will be small enough to ensure balance between each arm throughout the trial. The randomization list will be prepared by our pharmacy. The patients, treating physicians, and outcome assessors will be blinded to assigned treatment. Our pharmacy will prepare an opaque covering over each fluid bag within study kits, which will not be removed during the infusion to maintain blinding. Each bag will be labelled with a kit number and scannable bar code to ensure the patient receives study fluid as ordered which will be entered on their Medication Administration Record (Figure 1).

**Figure 1.** Image of Blinded Fluid Bag from Pharmacy

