### ***Sample size for Pilot Trial***

For the full-scale trial, a minimum of 43 participants must be recruited annually per site on average. The LHSC Victoria Campus ED treats approximately 130 patients with DKA annually, based on our hospital's Decision Support data from the most recent fiscal year (Mar 1 2019 – Feb 29 2020).

DKA by Site	Patients
Victoria Hospital	130
(E1010) Type 1 DM with ketoacidosis	70
(E1110) Type 2 DM with ketoacidosis	51
(E1112) Type 2 DM with keto & lactic acidosis	1
(E1410) Unspecified DM with ketoacidosis	8

Based on our research team hours of coverage (0700-2300) and past data from ED presentation time of potentially eligible patients, we expect to approach at least 104 (80%) of eligible patients in the one-year pilot study period, and a minimum of 43 approached participants (41.3%) must be recruited to meet the feasibility target. According to data from similar past trials, we

anticipate being able to recruit at least 50% of approached patients (target sample size of 52 patients, 26 in each arm). With 104 patients approached per year, a 90% two-sided confidence interval around the anticipated recruitment rate will have a total width of 0.17, i.e. a lower limit of 0.415 and an upper limit of 0.585. Because the lower limit excludes the minimum feasibility target of 41.3%, we can be 90% confident that the future trial is feasible.

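### The planning SD of 12.37 h carries the earlier study's unequal group sizes into a 1:1 trial; on the plan's own figures it should be 12.80 h, which raises the required N by about 7% for any fixed target difference

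*Combined protocol and SAP*

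**What the plan says.** The section *Sample size for Full-Scale Trial* takes its inputs from an earlier comparison of balanced crystalloids with saline in ED patients with DKA. It gives the quartiles by arm: "In the balanced crystalloids group (n=94), the median time to resolution of DKA was 13.0 hrs [IQR: 9.5-18.8" and "in the saline group (n=78) the median time to resolution was 16.9 hrs [IQR: 11.9-34.5". On the conversion to SDs it says: "The IQR was used to calculate the standard deviation for each group based on the following assumption for normally distributed data", that is, SD = IQR/1.35. It continues: "The pooled standard deviation was then calculated based on the sample size and standard deviation of each group" of that study. The formula printed there uses weights n − 1, and the result "and was determined to be 12.37".

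The size is then set "to achieve 80% power at the 5% level of significance with equal allocation" and 10% attrition, at 516 in total. The target reduction is 40% (6.76 h) in one sentence and 25% in the sentence that yields 516. The same section spreads 516 over 6 sites and 2 years: 86 per site, 43 per site-year. The section *Sample size for Pilot Trial* expresses 43 as a share of 104 approached patients (41.3%). It compares this with a 90% interval of 0.415 to 0.585 around an anticipated 50% and concludes that the future trial is feasible: "Because the lower limit excludes the minimum feasibility target of 41.3" per cent.

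**The concern.** Weighting two sample variances by their degrees of freedom is right when both estimate one common variance. The plan's own quartiles speak against that. The pooled figure then depends on how many patients the earlier study happened to have in each arm, and the larger arm there is the one with the smaller variance. A trial with equal allocation gives both variances the same weight, so 12.37 is too small for the design being planned.

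The effect is modest, but the pilot has little room for it. Its primary outcome is the recruitment rate, and the recruitment minimum comes directly from the full-scale N. The feasibility statement rests on a gap of 0.2 percentage points between 41.3% and 41.5%.

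**Working it through.** **Inputs** (all from *Sample size for Full-Scale Trial* unless noted): balanced crystalloids n = 94, IQR 9.5 to 18.8; saline n = 78, IQR 11.9 to 34.5; SD = IQR/1.35; 1:1 allocation; 5% significance, 80% power; 10% attrition; 6 sites, 2 years. The 104 approached patients and the lower limit of 0.415 are from *Sample size for Pilot Trial*.

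**1. Arm SDs.**
- Balanced: (18.8 − 9.5)/1.35 = 6.89 h
- Saline: (34.5 − 11.9)/1.35 = 16.74 h
- SD ratio 2.43; variance ratio 2.43² = 5.9

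**2. The plan's pooled SD.** sqrt((93 × 6.889² + 77 × 16.741²)/170) = 12.365. This reproduces 12.37.

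**3. The SD for a 1:1 comparison.** With n per arm, the variance of the mean difference is (SD1² + SD2²)/n. The usual formula writes it as 2·SD²/n, so SD² must be the simple mean of the two variances: sqrt((6.889² + 16.741²)/2) = 12.80. The variance ratio is (12.801/12.365)² = 1.072. N is proportional to SD², so N rises about 7% for any fixed difference.

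**4. Where 516 comes from.** I used n per arm = 2·SD²·(z_alpha + z_power)²/d², rounded up, divided by 0.90, rounded up and doubled. The text does not give enough to identify d or the sidedness for the full-scale trial, so I tried the candidates.

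| Difference d | Sides | N with 12.37 | N with 12.80 |
|---|---|---|---|
| 6.76 h (40% of 16.9) | 2 | 118 | 128 |
| 4.225 h (25% of 16.9) | 2 | 300 | 324 |
| 3.9 h (observed) | 2 | 352 | 378 |
| 3.25 h (25% of 13.0) | 2 | 508 | 544 |
| 2.86 h (6.76 − 3.9) | 1 | 516 | 552 |

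Only the last row returns 516 exactly: 2 × 12.37² × (1.645 + 0.842)²/2.86² gives 232 per arm, 232/0.90 gives 258, and the total is 516. This derivation is inferred from the arithmetic; the protocol does not state it. It is also doubtful in itself, because the expected difference (3.9 h) is smaller than the margin (6.76 h), and squaring hides the negative sign.

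**5. Carrying 12.80 through that row.** 248 per arm; 248/0.90 gives 276; total 552. 552/6 = 92 per site; 552/12 = 46 per site-year; 46/104 = 44.2%. This exceeds 41.5%. If 516 is kept (232 evaluable per arm), power in this calculation falls from 80.1% to 77.7%.

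**6. How much room the feasibility statement has.** 0.415 × 104 × 12 = 518. Any required N above about 518 puts the minimum above the stated lower limit.

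**The case against.** The strongest reply is that a reader might infer from this that 516, 43 per site-year and 41.3% are all too low and that the trial has less than its stated power. The documents do not support that. With the corrected SD and a two-sided test, the three differences that can be read most directly from the text (6.76, 4.225 and 3.9 h) need 128, 324 and 378, all below 516. At 232 evaluable per arm and SD 12.80, power is 99.99%, 94.5% and 90.7% respectively. For 4.225 h the recruitment minimum would be 324/12 = 27 per site-year, 26% of 104, and the feasibility statement would hold more easily. Only 25% taken of the balanced-arm median (3.25 h) or the inferred 2.86 h puts the corrected N above 516. This part of the reply stands.

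A reader might also infer that the 7% holds for any distribution. It does not. It rests on the variance ratio of 5.9, which comes from a normal-theory conversion applied to visibly skewed saline quartiles (11.9, 16.9, 34.5). The excess is ((1 + k)/2)/((93 + 77k)/170) − 1 for variance ratio k: 3.2% for k = 2 and 4.9% for k = 3. This stands too.

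On materiality, a chi-square 95% interval for a pooled SD of 12.37 on 170 degrees of freedom is about 11.2 to 13.8, which contains 12.80. The pilot itself is not powered on this SD, the anticipated 52 recruits still exceed 46, and the protocol allows for further sites. These facts limit the importance of the point. They do not make 12.37 the right input: imprecision in an estimate is no reason to weight it for a different design. A revision that settled the effect size but kept 12.37 would still come out about 7% short (300 instead of 324 at 4.225 h, for example).

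**Conclusion.** The weighting is wrong for the planned allocation. On the plan's own arm SDs the planning value is 12.80 h, not 12.37 h, and the required N for any fixed target difference is about 7% higher. This rests on the protocol's IQR/1.35 conversion and on 1:1 allocation.

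The consequences for 516, 43 and 41.3% are conditional. If the inferred one-sided 2.86 h calculation is retained, they become 552, 46 and 44.2%; the minimum then lies above the stated lower limit, or power at 516 is about 78%. If one of the larger stated effects is what was meant, 516 is more than enough even with 12.80. The direction of any error in 516 is therefore open until the 40% and 25% statements and the sidedness are reconciled. The SD should be corrected in the same revision, because the feasibility statement as written cannot absorb a 7% rise in N.

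**What to change.** In *Sample size for Full-Scale Trial*, replace 12.37 by 12.80 and describe it as the root of the simple mean of the two arm variances, matching equal allocation. In the same paragraph state the single target difference and the sidedness used, so that N can be reproduced. Recompute N and carry it through *Sample Size*, the per-site figures, and the recruitment minimum and its comparison with the lower limit in *Sample size for Pilot Trial*. Alternatively, keep 516 and restate its power.

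Where the protocol says that the pilot's attrition rate will inform the full-scale sample size, add that both arm SDs will be re-estimated from the pilot and averaged with equal weight, noting that they will be imprecise with about 26 patients per arm.

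The cost is restated planning figures only; the conduct of the pilot does not change. The downside is that the full-scale N and the pilot's recruitment minimum may become less favourable.

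### The full-trial sample size of 516 is attached to a 40% reduction in one section and a 25% reduction in the next, and on the plan's own inputs neither yields 516; the pilot's 41.3% recruitment threshold is built on it

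*Combined protocol and SAP*

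**What the plan says.** The Sample Size section gives 516 participants (258 per arm) for the full trial, assuming 5% alpha, 80% power, 1:1 allocation, "a 40% (6.76 hours) minimal clinically important reduction in DKA resolution time, and 10% attrition rate". It continues: "Based on this, the sample size for this local pilot RCT is 52 participants (26 per arm".

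The section Sample size for Full-Scale Trial takes medians and IQRs from an earlier comparison of balanced crystalloids with saline, which "found an absolute reduction in time to DKA resolution of 3.9 hours". It converts the IQRs to SDs and pools them to 12.37. It then says that "a superiority margin for a clinically significant difference was chosen to be a 40% (=6.76 hours) reduction in time to resolution of DKA". It concludes that "to achieve 80% power at the 5% level of significance with equal allocation", the total, "while accounting for a 10% loss to follow up and a 25% reduction in time to DKA resolution, is 516 participants (258 per group".

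No formula is printed, only a pointer to an external calculator. Neither section says whether the test is one- or two-sided.

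The total is then used: six sites over two years "would require an average minimum recruitment of 86 participants per site (43 per site per year". Sample size for Pilot Trial sets 43 against 104 patients approached, giving the 41.3% minimum. It notes that the lower limit of the expected 90% interval (0.415) lies above that minimum, and states 90% confidence that the full trial is feasible.

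**The concern.** Power, alpha, allocation and attrition are the same in both sections, so one total cannot answer to two different effect sizes. The role of 6.76 h also changes. In one section it is the smallest reduction judged clinically important, which would normally be the target difference. In the next it is a superiority margin, which enters a sample size formula in another way.

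Recruitment rate is the pilot's primary feasibility outcome, and its benchmark is derived directly from 516. If the total does not follow from the effect it names, a reader cannot tell which full trial the 41.3% threshold is meant to support.

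**Working it through.** **Inputs** (Sample Size; Sample size for Full-Scale Trial; Sample size for Pilot Trial): saline median 16.9 h, IQR 11.9 to 34.5, n = 78; balanced crystalloid median 13.0 h, IQR 9.5 to 18.8, n = 94; SD = IQR/1.35; power 80%; alpha 5%; attrition 10%; 6 sites, 2 years; 104 approached.

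**Reproducing the printed SD and base.** SDs are 9.3/1.35 = 6.89 and 22.6/1.35 = 16.74. The pooled SD is √[(93 × 6.89² + 77 × 16.74²)/170] = 12.365, which agrees with 12.37. 6.76/16.9 = 0.40 exactly, so the 40% is taken from the saline median. On that base, 25% is 4.225 h.

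**Test against zero.** n per arm = 2(z_α + z_β)² SD²/d², rounded up, then divided by 0.9 and rounded up. (z_α + z_β)² is 7.8489 two-sided and 6.1826 one-sided; SD = 12.37.

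| Difference d | Sides | n per arm | After attrition | Total |
|---|---|---|---|---|
| 6.76 h (40% of 16.9) | two | 52.6 → 53 | 59 | 118 |
| 6.76 h | one | 42 | 47 | 94 |
| 4.225 h (25% of 16.9) | two | 134.6 → 135 | 150 | 300 |
| 4.225 h | one | 106 | 118 | 236 |
| 3.9 h (observed) | two | 157.9 → 158 | 176 | 352 |
| 3.25 h (25% of 13.0) | two | 227.4 → 228 | 254 | 508 |

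Neither stated reduction gives 516 on the 16.9 h base. The last row comes near, but it is not exact and it changes the base from the one behind 6.76 h.

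**The only exact match found.** Take the gap between margin and observed difference, 6.76 − 3.9 = 2.86 h, one-sided 5%: 231.3 → 232 per arm, 232/0.9 → 258, total 516. This is inferred, since the plan prints no such step. If it was used, it is invalid: the expected benefit (3.9 h) is below the margin (6.76 h), and squaring the gap hides its sign.

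**What 516 gives in a two-sided test against zero.** With 232 evaluable per arm, SE = 12.37 × √(2/232) = 1.1485 h. The difference detected with 80% power is (1.960 + 0.842) × 1.1485 = 3.22 h, or 19.0% of 16.9 h. Power is 92.4% for 3.9 h, 95.7% for 4.225 h and above 99.9% for 6.76 h.

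**Effect on the threshold** (total/12 site-years, rounded up, over 104): 516 gives 43, 41.3%; 300 gives 25, 24.0%; 118 gives 10, 9.6%.

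**Sensitivity to the SD**, 25% of 16.9 h, two-sided:
- SD 12.37: 300.
- Each arm's own SD, √[(6.89² + 16.74²)/2] = 12.80: 145 → 162 per arm, total 324.
- Saline SD of 16.74 in both arms, a worst case: 247 → 275 per arm, total 550.

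**The case against.** The strongest reply is that the error lies in the planned size of a later trial. The pilot target of 52 is 50% of 104, and the pilot is expressly not powered for treatment differences. No stopping rule hangs on 41.3%, further sites may be added, and "The actual attrition rate determined by this pilot study will inform the sample size calculation for the full-scale multicentre study". All of this stands and limits the severity. It does not remove the point: updating attrition leaves the effect size unresolved, and extra sites do not say which effect 516 was meant to detect.

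It can also be said that the 25% has no stated base, and that on 13.0 h the total is 508, close to 516. That is fair, so the finding of non-reproduction is confined to the 16.9 h base.

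Three stronger readings are tempting but not supported:

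- A reader might infer that the invalid margin calculation was actually used. The match is exact, but the subtraction and the one-sided alpha appear nowhere in the plan.
- A reader might infer that a one-sided calculation contradicts the two-tailed t-tests in Data Analysis. Those tests are specified for the pilot, and the one-sided route is only inferred. What the documents show is that the full trial's sidedness is not stated.
- A reader might infer that the threshold is too lenient, since 550 would need 46 per site-year (44.2% of 104), above the 0.415 lower limit. That requires the saline SD in both arms, although the plan's own data imply 6.89 in the balanced arm; each arm's own SD gives 324.

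**Conclusion.** Wrong as written, and should be fixed, but it does not block the pilot. The same 516 is tied to two incompatible reductions. With SD 12.37, 80% power, two-sided 5% and 10% attrition on the 16.9 h base, a test against zero needs 118 or 300, so 516 is 4.4 or 1.7 times what the named effects require.

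A reader might go further and infer that the statement of 90% confidence in feasibility cannot be interpreted. The documents do not support that. For both stated effects with the documented SD, the required share falls to 9.6% or 24.0%, so 41.3% errs on the strict side. The pilot's target, conduct and analysis are unaffected.

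The totals rest on a normal approximation and on an SD derived from skewed IQRs. The documents cannot settle which effect was intended.

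**What to change.** In Sample Size and Sample size for Full-Scale Trial, state one target difference and its base, whether the test is against zero or against a margin (if a margin, the assumed effect must exceed it), and the sidedness. Then take one of two routes:

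1. Recompute the total. Two-sided against zero with SD 12.37, it is 118 for 40%, 300 for 25% or 352 for 3.9 h. These are not equivalent choices. With 53 evaluable per arm, SE = 12.37 × √(2/53) = 2.40 h, so 118 gives only about 37% power if the true difference is 3.9 h (3.9/2.40 − 1.96 ≈ −0.34).
2. Keep 516 and state what it gives against zero, two-sided: 80% power for 3.22 h, 92.4% for 3.9 h and 95.7% for 4.225 h.

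Update the 86 per site, 43 per site-year, 41.3% and the 90% confidence statement to match. Show the total over a range of SDs (for 25%: 300, 324, and 550 labelled as a worst case). Reword the opening of the sentence that gives 52, which implies that 52 follows from 516 when it is 50% of 104.

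The cost is rewording and recalculation in the three sample size sections. The pilot target stays at 52.
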